11.4 Serious Adverse Event Collection Period

Serious adverse events will be reported to AbbVie from the time the physician obtains the patient's authorization to use and disclose information (or the patient's informed consent) until 30 days or 5 half-lives following the intake of the last dose of physician-prescribed treatment.

11.5 Serious Adverse Event Reporting

In the event of a serious adverse event, and additionally, any non-serious event of malignancy in patients 30 years of age and younger, whether related to study drug or not, the Investigator will notify AbbVie Drug Safety [REDACTED] within 24 hours of the site being aware of the event.

11.6 Pregnancy Reporting

In the event of a pregnancy occurrence in the patient, the physician will notify AbbVie Drug Safety [REDACTED] identified within 24 hours of the physician becoming aware of the pregnancy.

12.0 Plans for Disseminating and Communicating Study Results

At the end of the study, a report will be written by AbbVie. This report will contain a description of the objectives of the study, the methodology and its results and conclusions. The completed Data Recording Forms, Questionnaires and the study report are the confidential property of AbbVie and may not be released to unauthorized people in any form (publications or presentations) without the express written approval from AbbVie. The results of this PMOS may be published by AbbVie Limited or by any one of the participating investigators after agreement with AbbVie Limited.

Annex 1. Study Questionnaires

A. WHODAS 2.0 questionnaire 12-item version, self-administered

The World Health Organization Disability Assessment Schedule (WHODAS 2.0) is a generic assessment instrument developed to provide a standardized method for measuring health and disability across cultures. It was developed from a comprehensive set of International Classification of Functioning, Disability and Health (ICF) items that are sufficiently reliable and sensitive to measure the difference made by a given intervention. This is achieved by assessing the same individual before and after the intervention.

WHODAS 2.0 has been found to be useful for assessing health and disability levels in the general population through surveys and for measuring the clinical effectiveness and productivity gains from interventions.

WHODAS 2.0 captures the level of functioning in six domains of life:

- Domain 1: Cognition – understanding and communicating
- Domain 2: Mobility – moving and getting around
- Domain 3: Self-care – attending to one’s hygiene, dressing, eating and staying alone
- Domain 4: Getting along – interacting with other people
- Domain 5: Life activities – domestic responsibilities, leisure, work and school
- Domain 6: Participation – joining in community activities, participating in society.

For all six domains, WHODAS 2.0 provides a profile and a summary measure of functioning and disability that is reliable and applicable across cultures, in all adult populations.

WHODAS 2.0 provides a common metric of the impact of any health condition in terms of functioning. Being a generic measure, the instrument does not target a specific disease – it can thus be used to compare disability due to different diseases. WHODAS 2.0 also makes it possible to design and monitor the impact of health and health-related interventions. The instrument has proven useful for assessing health and disability levels in the general population and in specific groups (e.g. people with a range of different mental and physical conditions).

Aspects that make WHODAS 2.0 particularly useful are its sound theoretical underpinnings, good psychometric properties, numerous applications in different groups and settings, and ease of use. WHODAS 2.0 can be self-administered in around 5 minutes,

and administered through an interview in 20 minutes. The instrument is easy to score and interpret (Ustun, Kostanjsek, Chatterji, & Rehm, 2010).

WHODAS 2.0

WORLD HEALTH ORGANIZATION
DISABILITY ASSESSMENT SCHEDULE 2.0

12-item version, self-administered

This questionnaire asks about difficulties due to health conditions. Health conditions include diseases or illnesses, other health problems that may be short or long lasting, injuries, mental or emotional problems, and problems with alcohol or drugs.

Think back over the past 30 days and answer these questions, thinking about how much difficulty you had doing the following activities. For each question, please circle only one response.

In the past 30 days, how much difficulty did you have in:						
S1	Standing for long periods such as 30 minutes ?	None	Mild	Moderate	Severe	Extreme or cannot do
S2	Taking care of your household responsibilities ?	None	Mild	Moderate	Severe	Extreme or cannot do
S3	Learning a new task , for example, learning how to get to a new place?	None	Mild	Moderate	Severe	Extreme or cannot do
S4	How much of a problem did you have joining in community activities (for example, festivities, religious or other activities) in the same way as anyone else can?	None	Mild	Moderate	Severe	Extreme or cannot do
S5	How much have you been emotionally affected by your health problems?	None	Mild	Moderate	Severe	Extreme or cannot do

In the past 30 days, how much difficulty did you have in:						
S6	Concentrating on doing something for ten minutes ?	None	Mild	Moderate	Severe	Extreme or cannot do
S7	Walking a long distance such as a kilometre [or equivalent]?	None	Mild	Moderate	Severe	Extreme or cannot do
S8	Washing your whole body ?	None	Mild	Moderate	Severe	Extreme or cannot do
S9	Getting dressed ?	None	Mild	Moderate	Severe	Extreme or cannot do
S10	Dealing with people you do not know ?	None	Mild	Moderate	Severe	Extreme or cannot do
S11	Maintaining a friendship ?	None	Mild	Moderate	Severe	Extreme or cannot do
S12	Your day-to-day work ?	None	Mild	Moderate	Severe	Extreme or cannot do

H1	Overall, in the past 30 days, how many days were these difficulties present?	Record number of days ____
H2	In the past 30 days, for how many days were you totally unable to carry out your usual activities or work because of any health condition?	Record number of days ____
H3	In the past 30 days, not counting the days that you were totally unable, for how many days did you cut back or reduce your usual activities or work because of any health condition?	Record number of days ____

This completes the questionnaire. Thank you.

B. Kessler Psychological Distress Scale (K10)

This is a 10-item questionnaire intended to yield a global measure of distress based on questions about anxiety and depressive symptoms that a person has experienced in the most recent 4 week period.

K10 Test

These questions concern how you have been feeling over the past 30 days. Tick a box below each question that best represents how you have been .

1. During the last 30 days, about how often did you feel tired out for no good reason?				
1. None of the time	2. A little of the time	3. Some of the time	4. Most of the time	5. All of the time
2. During the last 30 days, about how often did you feel nervous?				
1. None of the time	2. A little of the time	3. Some of the time	4. Most of the time	5. All of the time
3. During the last 30 days, about how often did you feel so nervous that nothing could calm you down?				
1. None of the time	2. A little of the time	3. Some of the time	4. Most of the time	5. All of the time
4. During the last 30 days, about how often did you feel hopeless?				
1. None of the time	2. A little of the time	3. Some of the time	4. Most of the time	5. All of the time
5. During the last 30 days, about how often did you feel restless or fidgety?				
1. None of the time	2. A little of the time	3. Some of the time	4. Most of the time	5. All of the time
6. During the last 30 days, about how often did you feel so restless you could not sit still?				
1. None of the time	2. A little of the time	3. Some of the time	4. Most of the time	5. All of the time
7. During the last 30 days, about how often did you feel depressed?				
1. None of the time	2. A little of the time	3. Some of the time	4. Most of the time	5. All of the time
8. During the last 30 days, about how often did you feel that everything was an effort?				
1. None of the time	2. A little of the time	3. Some of the time	4. Most of the time	5. All of the time
9. During the last 30 days, about how often did you feel so sad that nothing could cheer you up?				
1. None of the time	2. A little of the time	3. Some of the time	4. Most of the time	5. All of the time
10. During the last 30 days, about how often did you feel worthless?				
1. None of the time	2. A little of the time	3. Some of the time	4. Most of the time	5. All of the time

C. Health Assessment Questionnaire–Disability Index (HAQ-DI)

HEALTH ASSESSMENT QUESTIONNAIRE (HAQ-DI)©

Name: _____ Date: _____

Please place an “x” in the box which best describes your abilities OVER THE PAST WEEK:

	WITHOUT ANY DIFFICULTY	WITH SOME DIFFICULTY	WITH MUCH DIFFICULTY	UNABLE TO DO
DRESSING & GROOMING				
Are you able to:				
Dress yourself, including shoelaces and buttons?				
Shampoo your hair?				
ARISING				
Are you able to:				
Stand up from a straight chair?				
Get in and out of bed?				
EATING				
Are you able to:				
Cut your own meat?				
Lift a full cup or glass to your mouth?				
Open a new milk carton?				
WALKING				
Are you able to:				
Walk outdoors on flat ground?				
Climb up five steps?				

Please check any AIDS OR DEVICES that you usually use for any of the above activities:

 Devices used for Dressing (button hook, zipper pull, etc.)	 Built up or special utensils	 Crutches
 Special or built up chair	 Cane	 Wheelchair
	 Walker	

Please check any categories for which you usually need HELP FROM ANOTHER PERSON:

 Dressing and grooming	 Arising	 Eating	 Walking
--	----------------------------------	---------------------------------	----------------------------------

Please place an "x" in the box which best describes your abilities OVER THE PAST WEEK:

	WITHOUT ANY DIFFICULTY	WITH SOME DIFFICULTY	WITH MUCH DIFFICULTY	UNABLE TO DO
HYGIENE				
Are you able to:				
Wash and dry your body?				
Take a tub bath?				
Get on and off the toilet?				
REACH				
Are you able to:				
Reach and get down a 5 pound object (such as a bag of sugar) from above your head?				
Bend down to pick up clothing from the floor?				
GRIP				
Are you able to:				
Open car doors?				
Open previously opened jars?				
Turn faucets on and off?				
ACTIVITIES				
Are you able to:				
Run errands and shop?				
Get in and out of a car?				
Do chores such as vacuuming or yard work?				

Please check any AIDS OR DEVICES that you usually use for any of the above activities:

 Raised toilet seat	 Bathtub bar	 Long-handled appliances for reach
 Bathtub seat	 Long-handled appliances in bathroom	 Jar opener (for jars previously opened)

Please check any categories for which you usually need HELP FROM ANOTHER PERSON:

 Hygiene	 Reach	 Gripping and opening things	 Errands and chores
----------------------------------	--------------------------------	--	---

Your ACTIVITIES: To what extent are you able to carry out your everyday physical activities such as walking, climbing stairs, carrying groceries, or moving a chair?

COMPLETELY MOSTLY MODERATELY A LITTLE NOT AT ALL

Your PAIN: How much pain have you had IN THE PAST WEEK?
On a scale of 0 to 100 (where zero represents "no pain" and 100 represents "severe pain"), please record the number below.

Your HEALTH: Please rate how well you are doing on a scale of 0 to 100 (0 represents "very well" and 100 represents "very poor" health), please record the number below.

C. Short Quality of Life in Inflammatory Bowel Disease Questionnaire (IBDQ)

This questionnaire is designed to find out how you have been feeling during the last 2 weeks. You will be asked about symptoms you have been having as a result of your inflammatory bowel disease, the way you have been feeling in general, and how your mood has been. Please circle the number of your choice below each question.

1. How often has the feeling of fatigue or being tired and worn out been a problem for you during the past 2 weeks?
 1. All of the time
 2. Most of the time
 3. A good bit of the time
 4. Some of the time
 5. A little of the time
 6. Hardly any of the time
 7. None of the time
2. How often during the last 2 weeks have you delayed or canceled a social engagement because of your bowel problem?
 1. All of the time
 2. Most of the time
 3. A good bit of the time
 4. Some of the time
 5. A little of the time
 6. Hardly any of the time
 7. None of the time
3. As a result of your bowel problems, how much difficulty did you experience doing leisure or sports activities you would have liked to have done during the past 2 weeks?
 1. A great deal of difficulty; activities made impossible
 2. A lot of difficulty
 3. A fair bit of difficulty
 4. Some difficulty
 5. A little difficulty
 6. Hardly any difficulty
 7. No difficulty; the bowel problem did not limit sports or leisure activities
4. How often during the past 2 weeks have you been troubled by pain in the abdomen?
 1. All of the time
 2. Most of the time
 3. A good bit of the time
 4. Some of the time
 5. A little of the time

6. Hardly any of the time
 7. None of the time
 5. How often during the past 2 weeks have you felt depressed or discouraged?
 1. All of the time
 2. Most of the time
 3. A good bit of the time
 4. Some of the time
 5. A little of the time
 6. Hardly any of the time
 7. None of the time
 6. Overall, in the past 2 weeks, how much of a problem have you had with passing large amounts of gas?
 1. A major problem
 2. A big problem
 3. A significant problem
 4. Some problem
 5. A little trouble
 6. Hardly any trouble
 7. No trouble
 7. Overall, in the past 2 weeks, how much of a problem have you had maintaining or getting to the weight you would like to be?
 1. A major problem
 2. A big problem
 3. A significant problem
 4. Some problem
 5. A little trouble
 6. Hardly any trouble
 7. No trouble
 8. How often during the past 2 weeks have you felt relaxed and free of tension?
 1. All of the time
 2. Most of the time
 3. A good bit of the time
 4. Some of the time
 5. A little of the time
 6. Hardly any of the time
 7. None of the time
 9. How much of the time during the past 2 weeks have you been troubled by a feeling of having to go to the bathroom even though your bowels were empty?
 1. All of the time
 2. Most of the time
-

3. A good bit of the time
4. Some of the time
5. A little of the time
6. Hardly any of the time
7. None of the time

10. How often during the past 2 weeks have you felt angry as a result of your bowel problem?

1. All of the time
2. Most of the time
3. A good bit of the time
4. Some of the time
5. A little of the time
6. Hardly any of the time
7. None of the time

D. Dermatology Life Quality Index

DERMATOLOGY LIFE QUALITY INDEX

Hospital No: _____ Date: _____
 Name: _____ Score:
 Address: _____ Diagnosis: _____

DLQI

The aim of this questionnaire is to measure how much your skin problem has affected your life OVER THE LAST WEEK. Please tick one box for each question.

- | | | | |
|-----|--|-------------------------------------|---------------------------------------|
| 1. | Over the last week, how itchy, sore, painful or stinging has your skin been? | Very much  | |
| | | A lot  | |
| | | A little  | |
| | | Not at all  | |
| 2. | Over the last week, how embarrassed or self conscious have you been because of your skin? | Very much  | |
| | | A lot  | |
| | | A little  | |
| | | Not at all  | |
| 3. | Over the last week, how much has your skin interfered with you going shopping or looking after your home or garden? | Very much  | |
| | | A lot  | |
| | | A little  | |
| | | Not at all  | Not relevant  |
| 4. | Over the last week, how much has your skin influenced the clothes you wear? | Very much  | |
| | | A lot  | |
| | | A little  | |
| | | Not at all  | Not relevant  |
| 5. | Over the last week, how much has your skin affected any social or leisure activities? | Very much  | |
| | | A lot  | |
| | | A little  | |
| | | Not at all  | Not relevant  |
| 6. | Over the last week, how much has your skin made it difficult for you to do any sport? | Very much  | |
| | | A lot  | |
| | | A little  | |
| | | Not at all  | Not relevant  |
| 7. | Over the last week, has your skin prevented you from working or studying? | Yes  | |
| | | No  | Not relevant  |
| | If "No", over the last week how much has your skin been a problem at work or studying? | A lot  | |
| | | A little  | |
| | | Not at all  | |
| 8. | Over the last week, how much has your skin created problems with your partner or any of your close friends or relatives? | Very much  | |
| | | A lot  | |
| | | A little  | |
| | | Not at all  | Not relevant  |
| 9. | Over the last week, how much has your skin caused any sexual difficulties? | Very much  | |
| | | A lot  | |
| | | A little  | |
| | | Not at all  | Not relevant  |
| 10. | Over the last week, how much of a problem has the treatment for your skin been, for example by making your home messy, or by taking up time? | Very much  | |
| | | A lot  | |
| | | A little  | |
| | | Not at all  | Not relevant  |

Please check you have answered EVERY question. Thank you.

©AY Finlay, GK Khan, April 1992 www.dermatology.org.uk, this must not be copied without the permission of the authors.

E. Work Productivity and Activity Impairment Questionnaire: General Health V2.0 (WPAI:GH)

The following questions ask about the effect of your health problems on your ability to work and perform regular activities. By health problems we mean any physical or emotional problem or symptom. *Please fill in the blanks or circle a number, as indicated.*

1. Are you currently employed (working for pay)? _____NO _____YES

[figure not shown]
If NO, check "NO" and skip to question 6.

The next questions are about the **past seven days**, not including today.

2. During the past seven days, how many hours did you miss from work because of your health problems? *Include hours you missed on sick days, times you went in late, left early, etc., because of your health problems. Do not include time you missed to participate in this study.*
_____HOURS
3. During the past seven days, how many hours did you miss from work because of any other reason, such as vacation, holidays, time off to participate in this study?
_____HOURS
4. During the past seven days, how many hours did you actually work?
_____HOURS (*If "0," skip to question 6.*)
5. During the past seven days, how much did your health problems affect your productivity while you were working?

Think about days you were limited in the amount or kind of work you could do, days you accomplished less than you would like, or days you could not do your work as carefully as usual. If health problems affected your work only a little, choose a low number. Choose a high number if health problems affected your work a great deal.

Consider only how much health problems affected productivity while you were working.

[figure not shown]

CIRCLE A NUMBER

6. During the past seven days, how much did your health problems affect your ability to do your regular daily activities, other than work at a job?

By regular activities, we mean the usual activities you do, such as work around the house, shopping, childcare, exercising, studying, etc. Think about times you were limited in the amount or kind of activities you could do and times you accomplished less than you would like. If health problems affected your activities only a little, choose a low number. Choose a high number if health problems affected your activities a great deal.

Consider only how much health problems affected your ability to do your regular daily activities, other than work at a job.

CIRCLE A NUMBER

F. Flourishing Scale

The Flourishing Scale consists of eight items describing important aspects of human functioning ranging from positive relationships, to feelings of competence, to having meaning and purpose in life. The scale was called Psychological Well-being in an earlier publication, but the name was changed to more accurately reflect the content because the scale includes content that goes beyond psychological well-being narrowly defined.

Flourishing Scale

Below are eight statements with which you may agree or disagree. Using the scale provided, indicate your agreement with each statement by choosing the appropriate score.

- 7 = Strongly agree
- 6 = Agree
- 5 = Slightly agree
- 4 = Neither agree nor disagree
- 3 = Slightly disagree
- 2 = Disagree
- 1 = Strongly disagree

- | | |
|--|-------|
| 1. I lead a purposeful and meaningful life | _____ |
| 2. My social relationships are supportive and rewarding | _____ |
| 3. I am engaged and interested in my daily activities | _____ |
| 4. I actively contribute to the happiness and well-being of others | _____ |
| 5. I am competent and capable in the activities that are important to me | _____ |
| 6. I am a good person and live a good life | _____ |
| 7. I am optimistic about my future | _____ |
| 8. People respect me | _____ |
| Total | _____ |

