9.5 Data Sources

Designated investigator staff will collect data required by the protocol on paper Case Report Forms (CRFs). Collection of data includes but not limited to subject demographics, adverse events, serious adverse events and concomitant medications. Designated investigator staff should not enter any data until they have completed appropriate training. The sites are requested to send a copy of the CRF (scanned copy is acceptable) through to the Data Manager to enter into the database within 10 working days. Where there are discrepancies with the data, data clarification forms should be raised for the designated investigator staff to clarify and return to the Sponsor.

9.5.1 Questionnaires:

Subject self-assessment questionnaires will be utilized in this study to determine patients' improvement over time. Patients will require Internet access as the questionnaires are administered electronically through an online portal. For patients unable to utilize the online questionnaires paper-and-pencil versions of questionnaires will be provided and can be self-administered in person in a quiet and private area of the clinic. In addition, for subjects completing paper and pencil versions, the questionnaires can be administered over the telephone if the questionnaire time-point does not coincide with a clinic visit. Data collected via paper and pencil versions of the questionnaires will be transcribed by site staff into the online portal on behalf of the patient. Data will be retrieved directly by the Data Manager for analysis. Based on a pilot evaluation of the study questionnaires in a small number of patients, they are expected to take approximately 10 minutes per visit, per subject, to administer. Patients should ensure that their subject number and the date the questionnaire was completed is entered onto the questionnaire.

Each patient will complete six (6) common questionnaires at Baseline, Month 2, Month 4 and Month 6:

- WHODAS 2.0
 - Covers six different domains: cognition, mobility, self-care, getting along, life activities and participation.
 - Does not have a set cut point to define disability
 - 12 items

- WPAI:GH V2.0
 - This questionnaire looks at the effect of health problems on ability to work and perform regular activities.
 - Time missed from work, impairment of work
 - 6 items
- K10

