9.8.5 Secondary Efficacy Analyses

The following secondary endpoints will be analysed and summarised using general linear models and paired t-tests. The analyses summarising the changes across all indications will include participant, baseline levels and indication as terms in the analyses. Those analyses analysing changes within indications will use paired t-tests. Mean changes will be summarised with 95% confidence intervals derived from these analyses.

- Change in total WHODAS score 2 and 4 months after the initiation of adalimumab across all indications
- Change in total WHODAS score 6 months after the initiation of adalimumab in each indication
- Changes in WPAI:GI, K10, Flourishing Scale, and Subject Vitality Scale scores at 2, 4 and 6 months after the initiation of adalimumab, across all indications

- Change in disease-specific scores (HAQ-DI, SIBDQ, DLQI) at 2, 4 and 6 months after the initiation of adalimumab, in each indication

The proportion of patients at 6 months who remain on adalimumab, having satisfied the requirements for application for renewal of subsidy by special authority as defined below for each indication will be summarised for all indications combined and separately. These proportions will be summarised with exact 95% confidence intervals.

- **Rheumatoid arthritis:** $\geq 50\%$ decrease in active joint count from baseline AND a clinically significant response to treatment in the opinion of the physician
- **Crohn's disease:** CDAI score reduction by 100 points or CDAI score ≤ 150
- **Psoriasis:** PASI score reduction of $\geq 75\%$; or in the case of a patient had severe chronic plaque psoriasis of the face, or palm of a hand or sole of a foot at the start of treatment, the patient has a reduction in the PASI symptom subscores for all 3 of erythema, thickness and scaling, to slight or better, OR $\geq 75\%$ reduction in affected skin area.

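### SIBDQ item 8 is printed with codes that run opposite to the other nine items and no visible text reverses it, so summing the printed codes would mis-score this Crohn's disease secondary endpoint

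*Combined protocol and SAP*

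**What the plan says.** Annex 1 reproduces all ten SIBDQ items with numbered answers. The instruction to the patient is "Please circle the number of your choice below each question". Items 1 to 7, 9 and 10 ask about problems, with 1 as the worst answer and 7 as the best. Item 5, for example, asks "How often during the past 2 weeks have you felt depressed or discouraged" and runs from 1 (all of the time) to 7 (none of the time). Item 8 asks "How often during the past 2 weeks have you felt relaxed and free of tension" and carries the same labels in the same order.

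On the route to analysis, Section 9.5.1 makes the online portal the default. Paper answers "will be transcribed by site staff into the online portal on behalf of the patient", and then "Data will be retrieved directly by the Data Manager for analysis". The same section describes the SIBDQ as easy to score but gives no algorithm.

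Section 9.8.5 lists as a secondary analysis "Change in disease-specific scores (HAQ-DI, SIBDQ, DLQI) at 2, 4 and 6 months after the initiation of adalimumab, in each indication", with paired t-tests within an indication. Section 9.10 includes the secondary endpoints in the interim analysis. Sections 9.8 and 9.9 contain no scoring rule for the SIBDQ, no statement of score direction and no reversal of item 8.

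**The concern.** More relaxation is better health, so on item 8 the printed code falls as the patient improves. On the other nine items it rises. A plain sum of the printed codes would subtract points for improvement on item 8. The mean SIBDQ change in the Crohn's disease group and its confidence interval would then be biased at both the interim and the final analysis, in one of the two indications the study is powered for.

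The planned checks would not reveal this. Section 9.11 verifies the database against its sources, and the source form carries the same code. A range check would pass too, because ten codes between 1 and 7 always sum to between 10 and 70, whether or not item 8 is reversed.

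**Working it through.** The plan states no SIBDQ score, range or scoring rule, so there is no figure to reproduce. The check has four steps.

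**1. Direction of the items.** Three multi-item scales in Annex 1 show numbered answers.

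| Scale | Items | Wording | Items coded against their own scale |
|---|---|---|---|
| K10 (e.g. "During the last 30 days, about how often did you feel worthless") | 10 | all negative | 0 |
| SIBDQ | 10 | nine negative, item 8 positive | 1 (item 8) |
| Flourishing Scale ("Using the scale provided, indicate your agreement with each statement by choosing the appropriate score") | 8 | all positive | 0 |

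That is 10 + 10 + 8 = 28 items, of which one runs against its scale.

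**2. Effect on a single form, if printed codes are summed.** Let x be the printed answer to item 8 (1 to 7). The aligned score uses 8 − x; the printed score uses x.

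- Best state: aligned 10 × 7 = 70; printed 9 × 7 + 1 = 64.
- Worst state: aligned 10 × 1 = 10; printed 9 × 1 + 7 = 16.
- Span from worst to best: aligned 70 − 10 = 60; printed 64 − 16 = 48.
- Error per form: x − (8 − x) = 2x − 8, which is −6, −4, −2, 0, 2, 4, 6 for x = 1 to 7.

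**3. Effect on a change score.** The error is 2 × (x at follow-up − x at baseline).

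- It is zero if the answer does not change and at most 2 × 6 = 12 points either way.
- Each category of improvement on item 8 takes 2 points off the change score.
- A patient who goes from worst to best on all ten items shows +48 instead of +60.
- A patient who improves by k categories on item 8 alone shows −k instead of +k.

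**4. Illustration for a group mean.** The documents give no item-level changes, so these gains are assumed. Suppose the other nine items each improve by 1 point on average.

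| Mean gain on item 8 (categories) | Aligned change | Printed change | Relative error |
|---|---|---|---|
| 0 | 9 | 9 | none |
| 0.5 | 9.5 | 8.5 | −11% |
| 1 | 10 | 8 | −20% |
| 2 | 11 | 7 | −36% |

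For the paired t-test, assume equal gains and equal SDs across items and a common correlation r between item changes. The aligned sum then has mean proportional to 10 and variance proportional to 10 + 90r; the printed sum has 8 and 10 + 54r. The ratio of printed to aligned standardised effect is 0.8 × √[(10 + 90r)/(10 + 54r)]. With n = 80 and an aligned effect of 0.40 (the figures in Section 9.6, which are not specific to the SIBDQ), power with aligned scoring is 94.2%. With printed codes it is 80.7% at r = 0, 91.9% at r = 0.3, 93.1% at r = 0.5 and 94.2% at r = 1. Under these assumptions the main harm is a distorted mean change on a non-standard scale; loss of power is small unless the item changes are nearly uncorrelated.

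**The case against.** The strongest reply is that nothing in the plan says the printed codes will be summed. A positively worded item with an unchanged answer order is a way of collecting data, not a scoring rule. The SIBDQ is cited as a validated instrument, and its source may prescribe the reversal. The portal, which is the default route, may already store aligned codes; the instruction to circle a number comes from the form in Annex 1 and does not show what the portal stores. Nor is the silence peculiar to the SIBDQ: no scoring algorithm is visible for WHODAS 2.0, HAQ-DI, DLQI or WPAI:GH either, so the plan seems to leave scoring to the cited instruments. The 28-item count covers separate instruments and omits the Subject Vitality Scale, which is not visible in Annex 1.

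Much of this stands. Mis-scoring is not established, the cited source and the portal could not be examined, and the comparison with other scales shows only that the conflict is specific to this item. What it does not remove is that, for this item, the plan's own printed codes give the wrong direction if used as collected, and no planned check would show it. Relying on a programmer to reverse item 8 is not safe either: if the portal already stores it aligned, a routine reversal would create the error.

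**Conclusion.** The concern holds, as a minor and conditional point. Item 8 is printed against the direction of its scale, and no visible text corrects it. If the printed codes are summed, each form is off by 2x − 8 points (−6 to +6) and each change score by twice the change in the item 8 answer (at most 12 points either way). Where item 8 improves on average, the error works against showing benefit. No figure is claimed for the actual shift in the group mean, confidence interval or test, because that depends on item-level changes the documents do not give.

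The effect is confined to the SIBDQ in Crohn's disease. The interim results are not to influence study conduct (Section 9.10), so the consequence at the interim is limited to what is reported.

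**What to change.** Before the interim database lock (01 March 2016, Section 6.0), check how item 8 is displayed and stored in the portal, and how it is numbered on the paper form. Then add to Section 9.8.5 a statement along these lines:

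> SIBDQ items are scored so that 7 is the best state on every item. Where item 8 was stored with 1 = All of the time to 7 = None of the time, it is recoded as 8 minus the response before scoring; where it was already stored in the aligned direction it is left unchanged.

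This gives the right score whichever way the portal stores the item. The cost is one check of the portal and paper form, one statement in Section 9.8.5 and one conditional line of scoring code.
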